## 11.3 Planned Analysis

### 11.3.1 Disposition of patients

Number of patients having signed the informed consent form, receiving the study drug and by visit will be presented per cohort (CNS, vessels and other body regions), age group and overall.

Number of screen-failed patients and reasons for screening failure before study drug administration will be provided per cohort, age group and overall.

Number of injected patients prematurely discontinued from the trial and reasons for trial discontinuation will be provided according to the cohort, age group and overall.

### 11.3.2 Data Sets Analyzed

There will be four patient sets defined for this trial:

- The All enrolled patients set will include all patients having the informed consent form signed by their parent(s)/legal guardian (where applicable). This set will be used for patient disposition summaries and individual listings.
- The Full Analysis Set (FAS) will include all patients undergoing an enhanced MRI examination. This set will be used for the Efficacy Analysis.
- Safety Set will include all patients, receiving at least one administration of IMP. This set will be used for evaluation of safety, description of demographic data and baseline characteristics.
- The Per Protocol Set (PPS) will include all patients in the Safety Set without major deviations likely to impact the population PK model. This set will be used for population PK analysis and description of demographic data and baseline characteristics.

### 11.3.3 Protocol Deviations

As per International Conference on Harmonization (ICH) E3 guideline, a protocol deviation is any change, divergence or departure from the trial design or procedures defined in the protocol, with or without impact to the subject safety or the efficacy assessments.

Protocol deviations will be gathered from monitoring files, clinical database and external vendors of off-site data (laboratory data IWRS, ...).

Any deviation(s) from the original statistical plan will be described and justified in the final report. Protocol deviations will be split in major and non major deviations. A major deviation is defined as a deviation having an impact on the primary criteria. At minimum following protocol deviations will be stated as major in the trial:

- Patient not administered with gadopiclenol
- No plasma PK sample was obtained
- Concomitant treatment or procedure (e.g., diuretics, clinically significant blood loss or blood transfusion) that may alter gadopiclenol pharmacokinetic parameters
- All information regarding time of injection and times of PK sampling is missing

Other major deviations can be specified during the course of the trial and the exhaustive list of major and non-major deviations will be provided in the statistical analysis plan.

Patients with major deviations will be excluded from the PPS.

 CONFIDENTIAL	Protocol No. GDX-44-015 Version No. 4.0 including amendments 1 & 2 & 3 Date 09 Oct 2023	F015919-05 Page 61 / 75
---	---	----------------------------

PK modeling will be done using all patients of the PPS and sensitivity analyses could be conducted without data/patient identified as outliers.

Frequency and percentages of patients with non-major protocol deviations will be presented using the All enrolled Patients Set.

#### **11.3.4 Demographics and Baseline Characteristics**

All demographic and other baseline characteristics parameters will be summarised by cohort, age group and overall in the Safety Set and in PPS if different.

- Demographic parameters: age, sex, body weight, height, BMI, race/ethnicity.
- Other baseline characteristics: trial disease diagnosis, MRI examination, physical examination at screening, medical history, contrast media intolerance history and the prior medications / procedures defined as medications / procedures which stopped before IMP administration.

The main diagnosis will be coded using the MedDRA dictionary and tabulated by body system and preferred term

Patient's medical history will be coded using the MedDRA dictionary and tabulated by body system, preferred term and status (concomitant or not).

Patient's prior medications will be coded using the Anatomical Therapeutic Chemical (ATC) Drug dictionary and tabulated by ATC code.

Patient's prior procedures will be coded using the MedDRA dictionary and tabulated by body system, and preferred term.

#### **11.3.5 Compliance**

Volume theoretically administered (mL), volume actually administered (mL), theoretical volume actually administered (yes/no), absolute and relative difference between theoretical and actual volume will be displayed.

#### **11.3.6 Population PK analysis**

The population PK analysis will be performed on the PPS using a dedicated software modelling and including pharmacokinetic models library.

The structural model describing the gadopiclenol concentrations profile as a function of time and amount of product injected will be first determined. Structural PK model parameters will enter the model either as fixed or random effects (when supporting a between-patient variability).

Covariates potentially influencing the PK of gadopiclenol will be tested using a backward sequential approach in order to prevent inflation of the type I error over the number of statistical tests.

Quality of the model will be assessed using goodness of fit plots and an internal validation will be performed using visual predictive checks.

Gadopiclenol plasma concentrations below the limit of quantification will be considered as missing, unless their proportion represent more than 15% of the total concentrations. In that case, alternative methods, such as left-censoring, will be considered for their contribution to the likelihood.

Empirical Bayes estimates (EBEs) of PK parameters (basically clearance and volume of distribution) will be obtained from the final model and summarized per age group and overall. In addition, the following parameters will be derived from the EBES, depending on the structural model retained for gadopiclenol:

 CONFIDENTIAL	Protocol No. GDX-44-015 Version No. 4.0 including amendments 1 & 2 & 3 Date 09 Oct 2023	F015919-05 Page 62 / 75
---	---	----------------------------

- Area Under the Curve,
- Elimination half-life,
- Total clearance,
- Volume of distribution.

In addition, gadopiclenol plasma concentrations at 10, 20 and 30 minutes post-injection will be simulated from the final model and their distribution will be summarized using box-plots and descriptive statistics by cohort, age group and overall.

All methods to be applied for the population modelling will be fully detailed in a dedicated analysis plan.

### 11.3.7 *Efficacy Analyses*

All efficacy analyses will be done using the FAS and summarized per cohort and overall:

- Technical adequacy for diagnosis: results will be tabulated qualitatively for Pre and Paired (pre+post contrast) images. Shift tables between Pre and Paired scores will be provided.
- Assessment of overall contrast quality score will be tabulated qualitatively for Pre and Paired images. A shift tables between Pre and Paired scores will be provided.
- Evaluation of lesions/abnormal vessels: number and locations of detected lesions/abnormal vessels, and largest diameter (lesions only) of the 3 most representative lesions/abnormal vessels will be tabulated qualitatively and quantitatively respectively for Pre and Paired images.
- Assessment of contrast quality: signal intensity of lesion, percentage of enhancement (E%), LBR and CNR will be tabulated quantitatively.
- Lesion /vessel visualization (border delineation, internal morphology and contrast enhancement): for each parameter, score will be tabulated qualitatively for Pre and Paired images. A shift tables between Pre and Paired scores will be provided.
- Diagnosis (only for Pre MRI), diagnostic confidence, treatment plan for Pre and Paired MRI, change in diagnosis, change in diagnostic confidence and change in treatment plan from Pre to Paired MRI will be tabulated qualitatively.

### 11.3.8 *Adverse Event*

An overall summary of AEs will be presented using the All enrolled set to catch AEs of patients who did not receive trial drug. The table will be presented overall and only with the following variables:

- Total number of AEs
- Total number of patients with at least one AE
- Distribution of the number of AEs reported by patients (0, 1, 2 or 3 or more AEs)
- Total number of Serious AEs (SAEs)
- Total number of patients with at least one SAE
- Total number of AEs according to intensity (severity)
- Total number of patients with at least one AE according to intensity (severity)
- Total number of AEs according to the outcome
- Total number of patients with at least one AE according to the outcome
- Total number of AEs requiring a concomitant drug (other action taken)/procedure-Total number of patients with at least one AE requiring a concomitant drug (other action taken)/procedure

 CONFIDENTIAL	Protocol No. GDX-44-015 Version No. 4.0 including amendments 1 & 2 & 3 Date 09 Oct 2023	F015919-05 Page 63 / 75
---	---	----------------------------

- Total number of AEs leading to the patient's withdrawal from the study Events will be classified as treatment-emergent (TEAE) if they started after drug administration.

The same overall summary will be displayed by age group for Treatment Emergent AEs (TEAEs) using the Safety Set. The following variables will be also presented:

- Total number of TEAEs with causal relationship to the trial IMP.
- Total number of patients with at least one TEAE with causal relationship to the trial IMP.
- Total number of TEAEs requiring withdrawal of trial IMP.
- Total number of patients with at least one TEAE requiring withdrawal of trial IMP.

The number and percentage of patients with at least one TEAE will be presented using the Safety Set by age group according to Primary SOC and PT.

The number and percentage of patients with at least one TEAE with causal relationship to the IMP will be presented using the Safety Set by age group according to Primary SOC and PT.

The number and percentage of patients with at least one SAE or AESI will be presented using the Safety Set by age group according to Primary SOC and PT.

The number and percentage of patients with at least one SAE or AESI with causal relationship to the IMP will be presented using the Safety Set by age group according to Primary SOC and PT.

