 Any medication, including homeopathic products, over-the-counter medications, as well as prescription drugs, on-going at V1 or administered until V4 will be recorded in the patient's eCRF. Between V4 and V5 safety visits, newly started concomitant medications/treatments in patients experienced at least one AE will be documented. Any GBCA injection will be documented in all patients.

 At screening, blood sample will be collected to analyse biochemistry and hematology in central lab including measurement of serum creatinine and eGFR calculation. If centrally calculated eGFR is not available at V2, serum creatinine and eGFR can be obtained locally to confirm patient's eligibility, fingerstick capillary blood sampling at the point of care is acceptable.

Note: In any case the overall trial-related blood loss (including potential capillary blood sampling at the point of care for locally calculated eGFR) will not exceed the limit of 0.9 mL/kg body weight corresponding to 1% of total blood volume at a single time point and 2.4 mL/kg body weight (3% of the total blood volume during a period of four weeks).

 Contrast-enhanced MRI duration will correspond to the usual practice at site depending on the indication.

 All Adverse Events occurring from the beginning of the patient's participation in the trial (Informed Consent Form signature) and until V4, must be reported and followed even if no IMP was administered.

[figure not shown]
Non-serious AE occurring before IMP administration and not related to the trial can be collected as medical history or AE according to Investigator's opinion. Non-serious AEs occurring after V4 must be reported if related to the drug or to the trial and followed until recovery or sequelae stabilization.

 Serious Adverse Events (SAE) and Adverse Event of Special Interest (AESI) occurring from the beginning of the patient's participation in the trial (ICF signature) and until V5 must be reported and followed until recovery or sequelae stabilization (see [9.1.2](#)).

 Three blood samples will be drawn per patient, one during each time window: W1, W2 and W3 at time points allocated by randomization via IWRS.

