**Table 2: Collection and reporting of AEs throughout and after the trial.**

Visits and types of AEs to be reported	V1 - Screening Visit	V2 - Inclusion Visit	V3 - 1-day safety follow-up	V4 - 1-week safety follow-up	V5 - 3-month safety follow-up
	≤ 7 days before inclusion	D1	D2	D8±1day	D90±7days
Not related non-serious AEs	X*	X	X	X	
Not related SAEs	X	X	X	X	X
AESIs	X	X	X	X	X
Related**AEs (serious or not)	X	X	X	X	X

\* The events which occur before the first IMP administration, and which are not serious and not related to the trial procedures, might be recorded as medical history upon the Investigator's judgement.

\*\* related to the IMP and/or any protocol procedures including imaging procedures

As reminder, the patient's participation is defined as the period from the screening visit (ICF signature) to the last trial visit in the general case and defined in [10](#) in case of premature discontinuation.

Any AE is followed-up from its onset to recovery or stabilization of sequelae. If no follow-up is performed, the Investigator must provide a justification in the medical file and eCRF.

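### The Safety Set SAE/AESI table by SOC and PT in Protocol 11.3.8 is not limited to events after injection, so it can disagree with the treatment-emergent SAE count in the same section

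*Protocol*

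**What the plan says.** Protocol 11.3.8 (Adverse Event) sets the onset rule: "Events will be classified as treatment-emergent (TEAE) if they started after drug administration". It then applies the rule to three Safety Set outputs.

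- The overall summary: "The same overall summary will be displayed by age group for Treatment Emergent AEs (TEAEs) using the Safety Set". This repeats the variables of the All enrolled summary, which include the number of SAEs and the number of patients with at least one SAE.
- The general SOC/PT table: "The number and percentage of patients with at least one TEAE will be presented using the Safety Set by age group".
- The SOC/PT table of TEAEs related to the IMP.

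The next sentence drops the term: "The number and percentage of patients with at least one SAE or AESI will be presented using the Safety Set by age group", again by SOC and PT. A companion sentence covers SAEs/AESIs related to the IMP.

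Collection starts earlier than injection. Footnote 8 of the Trial Flow Chart says that SAEs and AESIs "occurring from the beginning of the patient's participation in the trial (ICF signature) and until V5 must be reported". Section 9.1.2, below Table 2, confirms that "the patient's participation is defined as the period from the screening visit (ICF signature) to the last trial visit". The note to Table 2 lets some early events be recorded as medical history instead, but only these: "The events which occur before the first IMP administration, and which are not serious and not related to the trial procedures". Section 11.3.2 defines the Safety Set by receipt of the IMP.

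**The concern.** A programmer who follows 11.3.8 literally would apply an onset filter to three of the Safety Set AE outputs and none to the SAE/AESI table. An SAE that began between consent and injection in an infant who was then dosed would enter a by-age-group safety table, although no gadopiclenol had been given. The safety objective in section 2.2 concerns the period after administration, so such an event does not bear on it.

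Two outputs on the same set, split by the same age groups, could then give different numbers of infants with an SAE, and 11.3.8 offers no rule to explain the gap. The trial has no control arm, and Group 3 may hold as few as five newborns, so a single event is visible in the percentages.

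**Working it through.** **1. Can a pre-injection SAE reach the table?** Each step rests on a stated rule.

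| Step | Source | Result |
|---|---|---|
| Is it collected? | Flow Chart footnote 8; Table 2 | Yes, from consent |
| How early can it start? | Section 3.3.1 | Up to 7 days before inclusion |
| Can it be moved to medical history? | Note to Table 2 | No, only non-serious events can |
| Does the Safety Set remove it? | Section 11.3.2 | No, if the infant was later dosed |
| Does the table sentence remove it? | Section 11.3.8 | No onset limit stated |
| Does the supplied SAP remove it? | SAP section 5 | No, it is the population PK plan and has no AE tables |

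**2. Which outputs are affected?**

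- Overall Safety Set summary by age group: limited to TEAEs, not affected.
- General and IMP-related TEAE tables: not affected.
- SAE/AESI table by SOC and PT: affected.
- IMP-related SAE/AESI table: in practice not affected, because section 9.1.3 classes events before administration as not related to the IMP.
- AESIs: in practice not affected. The only AESI is NSF (section 9.3.3), for which active detection is scheduled at the 3-month visit.

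**3. The plan's own figures.** The sample size reproduces: 45 evaluable / (1 − 0.10) = 50. The maximum participation reproduces: 7 screening days + Day 90 + 7 = 104 days. The minimum of 83 days is 90 − 7, that is, with no screening days.

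**4. Size of one case.** The shift is 1/n, with n taken from the stated minimum group sizes and the total of 50.

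| Group | n | Shift from one infant |
|---|---|---|
| Group 1 | 20 | 1/20 = 5.0 points |
| Group 2 | 12 | 1/12 = 8.3 points |
| Group 3 | 5 | 1/5 = 20.0 points |
| Overall | 50 | 1/50 = 2.0 points |

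The group figures are upper values. The minimums add to 20 + 12 + 5 = 37, so the other 50 − 37 = 13 infants must enlarge at least one group.

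**5. Illustration of the mismatch.** Suppose that Group 3 has five dosed newborns, and one had an SAE during screening, was still injected, and had no later SAE. No other newborn in the group has an SAE. The overall summary shows 0 of 5 with a treatment-emergent SAE. The SOC/PT table shows 1 of 5, or 20%.

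**6. How often?** The documents give no pre-injection SAE rate, so the expected number of cases cannot be computed. As a share of time, screening is at most 7 of 7 + 89 = 96 days, or 7.3%, with V5 on its nominal date, and it can be close to zero. This bounds exposure time. It is not an estimate of the share of SAEs.

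**The case against.** The strongest reply is that the plan already gives the right count. The overall Safety Set summary reports, by age group, the number of infants with a treatment-emergent SAE. A reader might infer from the loose sentence that the trial's main SAE result is inflated. The documents do not support that: the summary count is limited to events after injection, and so is the attribution to the IMP. Only one SOC/PT breakdown is open to the error.

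Cases should also be few. Eligibility is checked again before injection (8.1.2.1), an adverse event is a listed reason for screen failure (10.4), infants who are not injected fall outside the Safety Set, and hospitalisations planned beforehand without aggravation are not SAEs (9.2.1). A reader might take the 7.3% time share as the share of SAEs that are misplaced. That would need every infant to use the full screening window, a constant event rate, and no selection between the event and the injection. The documents establish none of these.

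Pre-injection events can also be traced: onset date and clock time are recorded (9.1.3), individual listings are planned (11.3.2), and the All enrolled summary includes SAEs before injection. But that summary is presented overall only, and mixes dosed with undosed infants, so it does not by itself explain a gap between two by-age-group Safety Set outputs.

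Finally, section 11 says that full detail is in a Statistical Analysis Plan. If a separate clinical plan exists, it may settle the matter, but it is not among the documents.

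These points limit the reach of the concern. None of them supplies the missing onset limit.

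**Conclusion.** The point stands as a narrow correction to one table rule. As written, the Safety Set SAE/AESI table by SOC and PT counts SAEs that began before injection in infants who were later dosed, and it can disagree with the treatment-emergent SAE count in the overall summary. That inconsistency follows from the wording and needs no assumed event rate.

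The effect per infant is at most 20 points in Group 3, 8.3 in Group 2 and 5 in Group 1, and 2 points overall. These figures assume Safety Set sizes equal to the stated minimums and 50 in total, and an infant with no SAE after injection. The number of such infants is unknown and probably small. The primary PK analysis and data collection are untouched.

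**What to change.** In Protocol 11.3.8, write *treatment-emergent SAE or AESI* in both Safety Set SAE/AESI sentences, using the onset definition already given there. The change to the IMP-related sentence is for consistency, since its content should not alter. Carry the same wording into any clinical analysis plan.

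Show SAEs that began before injection separately, alongside the All enrolled summary, and mark whether the infant was later dosed. The serious-event outputs can then be reconciled and no event is lost from the report.

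The cost is one onset filter in the table program and one extra line or listing. The onset date and time it needs are already collected, and no trial procedure changes.

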### **11.3.9 *Laboratory data***

Safety laboratory data are defined as laboratory variables centrally analyzed (hematology and biochemistry) from blood samples, estimated glomerular filtration rate (eGFR) centrally calculated based on the bedside Schwartz equation (see [7.2.1](#)). Safety laboratory data analysis will be done using the Safety Set.

The baseline is defined as the last measure before the IMP administration.

The statistical analysis will present results in Standard International (SI) units and conventional (CV) United States units. Original units will be only listed. Laboratory data will be analyzed quantitatively and qualitatively for each age group and overall. Qualitative analyses will be done via comparison of laboratory data to their reference ranges and according to their clinical significance. Quantitative analyses will be done by tabulating raw data and change from baseline.

The incidence of out-of-range results as well as shifts from baseline will also be presented by age group and overall.

### **11.3.10 *Other safety observations***

Other safety observations analysis will be done using the Safety Set.

#### **11.3.10.1      Vital signs (temperature, blood pressure, pulse rate and peripheral (SpO2) oxygen saturation (SpO2))**

The baseline is defined as the last measure before the IMP administration.

Vital signs will be analyzed quantitatively and qualitatively for each age group and overall. Qualitative analyses will be done via comparison of vital signs data to their normal ranges and according to their clinically significant changes. Quantitative analyses will be done by tabulating raw data and change from baseline.

 CONFIDENTIAL	Protocol No. GDX-44-015 Version No. 4.0 including amendments 1 & 2 & 3 Date 09 Oct 2023	F015919-05 Page 64 / 75
---	---	----------------------------

### 11.3.10.2 Injection site tolerance

Number of patients experiencing eruption, extravasation and inflammation at site injection will be tabulated by time point, per age group and overall.

### 11.3.10.3 Physical Examination

Any new abnormality since the previous visit will be tabulated by time point, per age group and overall.

